			CRP SI unit (unit: mg/L)	0, 3, 6, 12, 18, 24, 27 months	Treatment group	Continuous	Mean change from baseline (SD) (median, min, max if data are non-normal distributed), n
			ESR SI unit (unit: mm/h)	0, 3, 6, 12, 18, 24, 27 months	Treatment group	Continuous	Mean change from baseline (SD) (median, min, max if data are non-normal distributed), n
Vital signs	29A + 29B	29A. Intent-to-treat population 29B. Safety population	Weight (kg)	0, 3, 6, 12, 18, 24months	Treatment group	Continuous	Mean change from baseline (SD) (median, min, max if data are non-normal distributed), n

Table title	Number	Population	Endpoint	Time points or how to conglomerate	Covariates or subgroups	Type of variable	Summary statistics
			Height (cm)	0, 24 months	Treatment group	Continuous	Mean change from baseline (SD) (median, min, max if data are non-normal distributed), n
			Systolic blood pressure (mmHg)	0, 3, 6, 12, 18, 24 months	Treatment group	Continuous	Mean change from baseline (SD) (median, min, max if data are non-normal distributed), n
			Diastolic blood pressure (mmHg)	0, 3, 6, 12, 18, 24 months	Treatment group	Continuous	Mean change from baseline (SD) (median, min, max if data are non-normal distributed), n
			Heart rate per minute	0, 3, 6, 12, 18, 24 months	Treatment group	Continuous	Mean change from baseline (SD) (median, min, max if data are non-normal distributed), n

Table title	Number	Population	Endpoint	Time points or how to conglomerate	Covariates or subgroups	Type of variable	Summary statistics
Adherence	30A	Intent-to-treat population	% adherence according to pill count	3, 6, 12, 18, 24 months	Treatment group	Continuous	Mean (SD) (median, min, max if data are non-normal distributed), n
		Intent-to-treat population	% adherence according to electronic caps	3, 6, 12, 18, 24 months	Treatment group	Continuous	Mean (SD) (median, min, max if data are non-normal distributed), n
	30B	Per-protocol population	% adherence according to pill count	3 months	Treatment group	Continuous	Mean (SD) (median, min, max if data are non-normal distributed), n
		Per-protocol population	% adherence according to electronic caps	3 months	Treatment group	Continuous	Mean (SD) (median, min, max if data are non-normal distributed), n
	30C	Safety population	% adherence according to pill count	3, 6, 12, 18, 24 months	Treatment group	Continuous	Mean (SD) (median, min, max if data are non-normal distributed), n
		Safety population	% adherence according to electronic caps	3, 6, 12, 18, 24 months	Treatment group	Continuous	Mean (SD) (median, min, max if data are non-normal distributed), n

Table title	Number	Population	Endpoint	Time points or how to conglomerate	Covariates or subgroups	Type of variable	Summary statistics
Concomitant medications summary	31	Intent-to-treat population	Concomitant medication summary	Baseline	Treatment group	Dichotomous/continuous -DMARDs: % (n) -NSAIDs: % (n) -Biologicals: % (n) -Other anti-rheumatic medication: % (n) -Other medication:	Mean number (SD) (median, min, max if data are non-normal distributed) -Top 3 of most common concomitant medication class: 1. % (n) 2. % (n) 3. % (n)

Table title	Number	Population	Endpoint	Time points or how to conglomerate	Covariates or subgroups	Type of variable	Summary statistics
Bone mass	32	Intent-to-treat population	Bone mass lumber spine	0, 24 months	Treatment group	Continuous	Mean (SD) + 95% CI (median, min, max if data are non-normal distributed), n
		Intent-to-treat population	Change in bone mass lumbar spine	0-24 months	Treatment group	Continuous	Mean (SD) + 95% CI (median, min, max if data are non-normal distributed), n
		Intent-to-treat population	Bone mass hip	0, 24 months	Treatment group	Continuous	Mean (SD) + 95% CI (median, min, max if data are non-normal distributed), n
		Intent-to-treat population	Change in bone mass hip	0-24 months	Treatment group	Continuous	Mean (SD) + 95% CI (median, min, max if data are non-normal distributed), n
		Intent-to-treat population	Number of patients with at least one incident compression fracture (by VFA or lateral spine films)	24 months	Treatment group	Dichotomous	% (n), yes

Table title	Number	Population	Endpoint	Time points or how to conglomerate	Covariates or subgroups	Type of variable	Summary statistics
		Intent-to-treat population	Number of incident compression fractures (by VFA or lateral spine films)	24 months	Treatment group	Continuous	Mean (SD) + 95% CI (median, min, max if data are non-normal distributed)
	33	Intent-to-treat population	Number of prevalent vertebral fractures	0 months	Treatment group	Continuous	Mean (SD) (median, min, max if data are non-normal distributed), n
	34	Intent-to-treat population	Distribution of % height loss in vertebrae with fractures	0- months	Treatment group	Continuous	Mean (SD) (median, min, max if data are non-normal distributed), n
Joint replacement surgery	35	Intent-to-treat population	Number of joint replacement surgeries	0, 3, 6, 9, 12, 15, 18, 21, 24 months	Treatment group	Continuous	n (%)

Table title	Number	Population	Endpoint	Time points or how to conglomerate	Covariates or subgroups	Type of variable	Summary statistics
AE, SAE, other AE of special interest summary	36A	Intent-to-treat population	Number of AEs, SAEs, other AEs of special interest	3, 24 months	Treatment group	Continuous	-Mean (SD) (median, min, max if data are non-normal distributed) -Top 3 of most common AE categories: 1. % (n) 2. % (n) 3. % (n)
	36B	Safety population	Number of AEs, SAEs, other AEs of special interest	3, 24 months	Treatment group	Continuous	-Mean (SD) (median, min, max if data are non-normal distributed) -Top 3 of most common AE categories: 1. % (n) 2. % (n) 3. % (n)
AEs, SAEs, other AEs of special interest	36C	Intent-to-treat population	Number of AE, SAE, other AE of special interest per organ system	3, 24 months	Treatment group	Categorical	-Category 1: n (%) -Category 2: (n%) -Category 3: n (%) Etc.

Table title	Number	Population	Endpoint	Time points or how to conglomerate	Covariates or subgroups	Type of variable	Summary statistics
36D	Safety population	Number of AE, SAE, other AE of special interest per organ system	3, 24 months	Treatment group	Categorical	-Category 1: n (%) -Category 2: (n%) -Category 3: n (%) Etc.	-Category 1: n (%) -Category 2: (n%) -Category 3: n (%) Etc.
37	Intent-to-treat population	Presence of SAE or other AE of special interest	24 months	Treatment group	Dichotomous	-Yes: n(%) -No: n(%)	

Figure 1 Patient disposition: consort flow chart

Figure 2 Premature discontinuation per treatment group: Kaplan-Meier survival curve

Figure 2 DAS28 score per treatment group over time

Figure 3 Number of SAEs and other AEs of special interest per treatment group : Kaplan-Meier survival curve

Figure 4 Probability density plot of x-rays at 0 and 24 months

Listing 1	Patient disposition
Listing 2	Patients excluded from the analysis populations
Listing 3	Protocol violations
Listing 4	Visit windows
Listing 5	Study completion including reason early withdrawal
Listing 6	Demographics and baseline characteristics
Listing 7	History of glaucoma and cataract
Listing 8	RA history
Listing 9.A	Medical history
Listing 9.B	Medical history with MedDRA Coding
Listing 10.A	Treatment not given according to protocol - interrupted
Listing 10.B	Treatment not given according to protocol – discontinued
Listing 11	Change of antirheumatic treatment, with reason
Listing 12	Intensification of treatment for existing comorbidity, e.g. hypertension or diabetes
Listing 13	DAS28 scores, DAS44 scores and EULAR response
Listing 14	Swollen and tender joints
Listing 15.A	Patient global assessment of disease
Listing 15.B	Physician global assessment of disease
Listing 16	ACR 20 response
Listing 17	Minimal disease activity
Listing 18	Total Sharp/van der Heijde damage score of hands and forefeet radiographs
Listing 19	Morning stiffness
Listing 20.A	SF-36 questionnaire
Listing 20.B	SF-36 scores
Listing 21.A	(m)HAQ questionnaire
Listing 21.B	(m)HAQ scores
Listing 22.A	RAID questionnaire
Listing 22.B	RAID scores
Listing 23.A	EQ-5D questionnaire
Listing 23.B	EQ-5D scores
Listing 24	Patient symptom list questionnaire
Listing 25.A	Laboratory – Hematology and chemistry
Listing 25.B	Laboratory – Lipids
Listing 25.C	Laboratory – CRP and ESR
Listing 26	Vital signs
Listing 27	Physical examination
Listing 28	Previous medication
Listing 29	Concomitant medications
Listing 30.A	Adverse events
Listing 30.B	Serious adverse events
Listing 30.C	Other adverse events of special interest
Listing 31	Death

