6.3 Exclusion criteria

A potential subject who meets any of the following criteria will be excluded from participation in this study:

Lower probability of benefit:

- Change, stop or start of antirheumatic treatment in the last month prior to eligibility assessment, including methotrexate, sulfasalazine, hydroxychloroquine, leflunomide, azathioprine, intramuscular and oral gold, cyclosporine, biologic agents including anti-TNF, anakinra, abatacept, rituximab, tocilizumab (temporary exclusion);
- Treatment with systemic GC: oral or parenteral GC with a cumulative prednisolone equivalent dose of 200 mg or higher in the last 3 months (temporary exclusion);
- Treatment with any GC (oral, intra-articular, intravenous or intramuscular) in the last 30 days (temporary exclusion);
- Note: as this is a pragmatic trial, patients who require start of (other) antirheumatic treatment *at baseline or during the trial* can still be eligible (see 7.2).

Higher probability of harm:

- Exposure to investigational therapy in the last three months;
- Current participation in another clinical trial;
- Major surgery, donation or loss of approximately 500 ml blood within 4 weeks prior to the screening visit (temporary exclusion)
- Absolute contraindication to low-dose prednisolone, as determined by the treating physician, such as: uncontrolled chronic infections, diabetes mellitus, hypertension, osteoporosis. When these conditions are under control (e.g. with antiosteoporosis drugs, antihypertensive drugs) these patients can enter;
- Absolute contraindication to Calcium and/or Vitamin D supplement as determined by the treating physician, such as: hyperparathyroidism (when insufficiently treated);

- Uncontrolled comorbid conditions, short life span, etc. as determined by the treating physician.

Difficulty to measure harm/benefit:

- Absolute indication to start with oral or intravenous GC, according to the treating physician;
- Inability to comply with medical instructions or inability to assess major outcomes at 6-monthly visits, in the assessment of the treating physician.

Subjects/patients not capable or willing to provide informed consent.

Substudy

Additional exclusion criteria for subjects participating in the substudy to measure the effect of a reminder via smartphone on adherence:

Inability/difficulty to measure benefit:

- Not in the possession of a smartphone;
- Premature discontinuation of study medication within or at 3 months of the main trial.

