#### 4.10.1.1 Full model

We model the treatment outcome by a mixed effect model with fixed effects measurement occasion after baseline (d), baseline measurement (Z), treatment condition (T), and random effects across individuals (level 2; random intercept U) and study centers (level 3; random intercept V).

Furthermore, we include the strata of the GLORIA trial (S) as fixed effects. Centers could also be modeled as fixed effects, but we have chosen random effects because several centers have included only a very low number of patients. A compound symmetry correlation structure is assumed.

We write down mixed effect model 1 as:

$$\begin{aligned}
 Y_{ijk} &= \beta_{0jk} + \sum_{s=1}^4 \beta_{1jks} d_{ijks} + \epsilon_{ijk} && \text{(level-1 model)} \\
 \beta_{0jk} &= \delta_{00k} + \delta_{01k} S_{jk1} + \delta_{02k} S_{jk2} + \delta_{03k} T_{jk} + \delta_{04k} Z_{jk} + U_{0jk} && \text{(level-2 model for intercept)} \\
 \beta_{1jks} &= \delta_{10ks} && \text{(level-2 model for slope)} \\
 \delta_{00k} &= \gamma_{000} + V_{00k} && \text{(level-3 model for intercept)} \\
 \delta_{01k} &= \gamma_{010} && \text{(level-3 model for slope)} \\
 \delta_{02k} &= \gamma_{020} && \text{(level-3 model for slope)} \\
 \delta_{03k} &= \gamma_{030} && \text{(level-3 model for slope)} \\
 \delta_{04k} &= \gamma_{040} && \text{(level-3 model for slope)} \\
 \delta_{10ks} &= \gamma_{100s} && \text{(level-3 model for slope)}
 \end{aligned}$$

with  $U_{0jk}$  the individual-level random effect,  $V_{00k}$  the center-level random effect, and  $\epsilon_{ijk}$  the residual.

The indices:

- i= 1,..., m : fixed measurement occasion after baseline (in GLORIA, m=5)
- j= 1,...,n : individuals
- k=1,...,K : study centers (currently, K=28 in GLORIA)

The variables:

- $Y_{ijk}$  : DAS28 outcome
- $d_{ijks}$  : dummy variables encoding the five measurement occasions after baseline, s=1,..., 4
- $T_{jk}$  : treatment indicator, 0 if placebo, 1 if active (prednisolone) treatment
- $Z_{jk}$ : Baseline measurement of DAS28
- $S_{jk1}, S_{jk2}$ : Stratification factors

The parameters:

- $\gamma_{000}$ : the model intercept
- $\gamma_{010}$ : fixed effect of stratification factor 1
- $\gamma_{020}$ : fixed effect of stratification factor 2
- $\gamma_{030}$ : fixed effect of treatment
- $\gamma_{040}$ : fixed effect of baseline measurement of DAS28
- $\gamma_{100s}$ : effect of time dummy s

And the random effects :

- $U_{0jk}$  : random intercept of individual i

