#### 4.13 Analysis of secondary outcome variables

We will estimate and test for the detrimental effects of prednisolone on bone mass and incident fracture rate.

1. Continuous outcomes: bone mass lumbar spine, bone mass hip: analyzed according to model 1
2. Discrete outcome: presence of at least one incident compression fracture (by VFA or lateral spine films): analyzed according to model 2

Tests will be one-sided at  $p < 0.05$ , with Benjamini-Hochberg adjustment for multiple testing.

We will report the results of the other secondary outcome variables descriptively with means/proportions and 95%CI per treatment group per time point.

3. Variables measured at every clinic visit
  - a. Continuous outcomes: patient and physician global assessment of disease activity, joint counts (swollen joints and tender joints), acute phase reactants (C-reactive protein (CRP) and erythrocyte sedimentation rate (ESR)); vital signs, lab (blood) variables; adherence by pill count and by electronic adherence cap.
  - b. Discrete outcomes: patients with at least one instance of remission; of minimal disease activity; patients with at least one long-term period (2 consecutive instances 6 months apart) of remission; of minimal disease activity
4. Variables measured at every visit (clinic and remote):
  - a. Continuous outcomes: severity and duration of morning stiffness, RA Impact of disease (total score, and components pain and fatigue analyzed separately), RAPID3 index, EuroQoL, m(HAQ)
  - b. Discrete outcomes: discontinuations of study drug, of with reason; all changes of antirheumatic treatment, with reason; joint replacement surgery
  - c. Expressed as survival curve: discontinuation of study drug over time
5. Variables measured at baseline and end of study:
  - a. Continuous outcomes: DAS44, SF36 (domains and summary mental and physical component scores), 57-symptom list;
  - b. Discrete outcome: number of incident compression fractures (by VFA or lateral spine films)
6. Variables measured only at baseline:
  - a. Continuous/discrete: Demographics, education and medical history; Morisky medication adherence scale (MMAS-8), health literacy, arthritis helplessness index questionnaires; number of prevalent vertebral fractures (by VFA or lateral spine films), distribution of % height loss in vertebrae with fractures.
7. Response indices calculated at 3 months in the PP analysis (discrete): ACR20, 50, 70; EULAR response.

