#### *Prednisone open label use*

The PD tracker was reconciled with the Conmeds page in the manual listings. This has been done after final coding. This list has been crossed checked with the PD tracker, and for all prohibited prednisolone open label use an PD form has been created. If this prohibited open label use took place in the 30 days before baseline, or between ICF signature date and V2, the patient is excluded

from the PP population (see prohibited meds sections). Other prednisolone open label use (after V2) will be flagged for analysis, but does not affect the PP selection.

In the coded conmeds file, the H02 ATC codes were selected. And the following rules were applied:

- IV GCs are always a Protocol Deviation (if before stop of IMP).
- Oral GCs are allowed for a maximum period of 3 weeks, for max 4 times, during IMP use.
- Intra-Articular and Intra Bursal are allowed a maximum of 4 times during IMP use
- Intra Muscular GCs are allowed to a maximum of 2 times during IMP use.

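### The formal bone-mass harm tests do not adjust for baseline anti-osteoporosis drug use: some avoidable imprecision, no bias

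*SAP*

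**What the plan says.** SAP 4.13 singles out three secondary outcomes for formal harm testing: lumbar bone mass, hip bone mass, and at least one incident compression fracture. The tests are one-sided at 0.05, "with Benjamini-Hochberg adjustment for multiple testing". The remaining secondary outcomes are descriptive. For the two bone-mass outcomes the instruction is "Continuous outcomes: bone mass lumbar spine, bone mass hip: analyzed according to model 1".

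Model 1 (SAP 4.10.1.1) contains treatment, measurement occasion, the baseline value of the outcome, and random intercepts for patient and centre. On design factors it adds: "Furthermore, we include the strata of the GLORIA trial (S) as fixed effects". It has no term for bone-active drugs.

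Protocol 9.2 balances allocation on site, prior glucocorticoid exposure and concurrent start of other antirheumatic therapy. Protocol 6.3 gives osteoporosis among its examples of an absolute contraindication if uncontrolled, and then says: "When these conditions are under control (e.g. with antiosteoporosis drugs, antihypertensive drugs) these patients can enter".

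Protocol 7.4 has all medication recorded in the eCRF. SAP Appendix C shows that it was coded: "In the coded conmeds file, the H02 ATC codes were selected". Table 31 summarises baseline medication by class without a row for bone drugs. Table 32 describes bone mass, including "Change in bone mass lumbar spine", by treatment group.

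**The concern.** The trial is in patients aged 65 or over, and its entry rule expects some of them to be on drugs that act directly on the tested outcome. Two patients with the same baseline bone mass, one treated and one not, can be expected to change differently over two years. Baseline bone mass alone cannot separate them, since a low value may mark either untreated loss or current treatment. The variation due to drug use therefore stays in the residual.

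The SAP justifies one-sided harm testing by limited power (4.10). In a test meant to detect harm, giving up precision that already collected data could supply is worth avoiding. A null bone-mass result would also be hard to read if no table showed how many patients in each arm were on bone drugs.

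**Working it through.** **The plan's own figure.** There is none for bone mass. The only stated harm power concerns adverse events of special interest (34% v 46%, 400 patients, 80%). It recomputes to 79.1% one-sided, but says nothing about bone.

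**Model terms.** DEXA is done at 0 and 24 months (SAP 1.4.2), so there is one post-baseline value. Model 1 then reduces to treatment, baseline value, two strata and a centre intercept.

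**Assumed inputs, none in the documents.** Proportion on a bone drug at baseline p = 10-40%; drug effect on two-year lumbar change d = 0.02-0.04 g/cm2; SD of change 0.045 g/cm2; 150 scan pairs per arm; prednisolone difference 0.009 g/cm2. Power is for a single one-sided 5% test, before the Benjamini-Hochberg step.

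**Step 1, variance explained.** R2 = p(1-p)d^2 / SD^2, with SD^2 = 0.002025.
- Low: 0.10 x 0.90 x 0.0004 / 0.002025 = 0.018
- Middle: 0.25 x 0.75 x 0.0009 / 0.002025 = 0.083
- High: 0.40 x 0.60 x 0.0016 / 0.002025 = 0.190

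The equivalent gain in patients, 1/(1-R2) - 1, is 1.8%, 9.1% and 23.4%. These are upper values, because the formula ignores overlap with baseline bone mass, which is already in the model.

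**Step 2, power.** Unadjusted SE = 0.045 x sqrt(2/150) = 0.00520. Power = Phi(0.009/0.00520 - 1.645) = 53.5%. Adjusted SE = 0.00520 x sqrt(1-R2).
- Low: SE 0.00515, power 54.1%
- Middle: SE 0.00497, power 56.5%
- High: SE 0.00468, power 61.0%

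If all 225 patients per arm had scan pairs, the middle case would go from 68.3% to 71.6%.

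**Step 3, a second parametrisation.** With 225 per arm, an effect set to give 80% power unadjusted, p from 10% to 50% and d from 0.3 to 1.0 residual SD, adjustment raises power to between 80.3% and 87.2%. At p = 20-30% and d = 0.5 it reaches 81.3-81.8%.

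**Step 4, bias.** In a simulation with 450 patients and 4,000 runs, 30% were users, d was 0.5 SD, and the prednisolone effect was -0.25 SD in non-users and zero in users. The true average is 0.70 x (-0.25) = -0.175. The mean estimate was -0.1750 without the covariate (SE 0.098) and -0.1756 with it (SE 0.095). With -0.25 in everyone, both gave -0.250. The covariate narrows the SE and leaves the estimate where it was.

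**Step 5, chance imbalance.** At p = 25% the SD of the between-arm difference in use is sqrt(2 x 0.1875/150) = 0.050, which moves the estimate by 0.050 x 0.03 = 0.0015 g/cm2. Since (0.0015/0.00520)^2 = 0.083, this is the same variance as in Step 1, not an additional loss. The unadjusted SE already includes it.

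**The case against.** The strongest case for the plan is that nothing in it is invalid. Allocation is randomised 1:1, the model is linear, and SAP section 2 states a treatment-policy aim in a trial built to resemble routine care. Adjustment buys only a few points of power, every input to that figure is assumed, and part of the gain may already be taken by baseline bone mass. Protocol 6.3 names bone drugs only as an example of control, requires none and gives no prevalence. Bone mass does not enter the success and failure rules of SAP 4.12. All of this stands, and it limits the point to a minor one.

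Three stronger readings are tempting, and the documents do not support them.

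- **That ignoring baseline bone drugs pulls the estimate toward no harm.** Step 4 shows otherwise. If users of bone drugs lose less bone on prednisolone, the smaller average is a true property of the enrolled population, and a main-effect covariate does not change it.
- **That an analysis of non-users would be the more powerful test.** With an effect of 0.012 g/cm2 in non-users, none in users and 25% users, the pooled test has 53.5% power and the non-user subgroup (112.5 per arm) 64%. If the effect is 0.012 in everyone, the pooled test has 75% and the subgroup still 64%. The ordering depends wholly on assuming no effect in users, and the subgroup answers a different question.
- **That Table 32 shows the model to be unadjusted.** Its covariate column lists only treatment group, but so does that of Table 9, the DAS28 mixed model, which does adjust. The evidence lies in SAP 4.13 and 4.10.1.1.

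On drugs started after baseline, the plan is not silent: Listings 12 and 29 carry treatment intensification and concomitant medication. They are patient listings, however, and promise no summary by arm of new bone-drug starts.

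**Conclusion.** The point holds as a missed precision covariate in two of the three formally tested secondary harm outcomes. The intent-to-treat estimate and the validity of the test are unaffected. Over the assumed range the covariate explains at most about 2-19% of the variance. At the central assumptions power rises by about 3 points, and in the second parametrisation by 1-2 points in mid-range. The true gain could be smaller and cannot be fixed from the documents. Severity is minor; the reason to act is that the change costs almost nothing.

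**What to change.** In SAP 4.13, before the blind is broken, add baseline anti-osteoporosis drug use (yes/no, derived from the ATC-coded baseline medication, with the code list stated) as a fixed effect in the lumbar and hip bone-mass models. Keep the formal test in the whole intent-to-treat set, one-sided with the planned multiplicity adjustment.

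Optionally, tabulate by arm the number of patients on such a drug at baseline and the number who start one over the 24 months, to help interpret a null result. An estimate in baseline non-users may be added as supportive, labelled as a different estimand.

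Cost: one derived variable from data already coded and one model degree of freedom, plus a table row or two if the optional counts are added.
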